4 SELECTION AND WITHDRAWAL OF PARTICIPANTS

4.1 Inclusion Criteria

Individuals who meet all of the following criteria are eligible for enrollment as study participants:

- Diagnosis of peanut allergy by medical history
- Evidence of peanut-specific IgE by either: positive skin prick test to peanut (reaction wheal at least 5 mm larger than saline control) or serum peanut-specific IgE ≥5 kU/L at screening visit.
- Ara h 2 specific IgE >0.35 kU/L at screening visit.
- Who are willing to sign informed consent or whose parent or legal guardian is willing to sign the consent form (age appropriate)
- Who are willing to sign the assent form, if age appropriate
- Males and females of all ethnic/racial groups aged 7-55 years old who are otherwise healthy.
- React to ≤443 mg of peanut protein during DBPCFC1

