7.4 Main Study Visits

7.4.1 Double-Blind Placebo-Controlled Food Challenge 1 (Day 28)

Participants will come to the MGH CRC four weeks (± 4 days) after the baseline visit for a double-blind, placebo -controlled food challenge (DBPCFC1) to peanut. In a DBPCFC, two challenges, one containing placebo material (toasted oat flour) and one containing peanut flour will be performed on two days within a two week period. The order of challenge will be determined by coin toss by the dietitian and will be unknown to the study nurse, investigator, and study participant. The MGH CRC dietician will prepare the challenge materials. Details of the DBPCFC procedure are below in section 7.7.1.

Prior to each challenge, the participant will have a physical exam with vital signs, spirometry, and an IV will be placed. A negative urine pregnancy test will be documented for female participants of child-bearing potential; if the test is positive, the visit will be cancelled and if pregnancy is confirmed, the subject will be withdrawn from the study. The participant will be required to have a baseline FVC and FEV1 >80% of their predicted values and an FEV1/FVC of >0.7 or the DBPCFC will be rescheduled. A study nurse who is blinded to the testing material will administer the challenge. The supervising physician will be present during the challenge and will also be blinded to testing material.

A member of the study staff will follow up with participant with a telephone call the day after the DBPCFC for active safety monitoring.

If the participant reacts at the 300 mg dose of peanut protein or less (443 mg cumulative), he/she will be randomized to receive active or placebo OIT.

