7.7 Study Procedures

7.7.1 Double-Blind Placebo-Controlled Food Challenge

In a DBPCFC, two challenges, one containing placebo oat flour and one containing peanut flour, will be performed. The dietitian will perform the preparation of the challenge materials. Prior to the food challenge, participants will be asked to restrict the use of antihistamines (short-acting, 72 hours: long-acting, 7 days), beta-agonists (12 hours), theophylline (12 hours), and cromolyn (12 hours). For DBPCFC1, one challenge will consist of 5 doses of peanut powder given every 20 minutes in increasing amounts up to a cumulative total of 443 mg of peanut protein masked by inclusion in vehicle food. Available vehicle foods will include rice milk, soymilk, mint chocolate mousse, or applesauce. The other challenge will consist of oat flour given also in 5 doses in an identical volume of vehicle food. For the active challenge, the first ingested dose will be 3 mg, then increasing to 10 mg, 30 mg, 100 mg, and 300 mg of peanut protein[?]. The placebo challenge doses will be the equivalent amount of oat flour by weight.

The protocol of the DBPCFC2 will be identical to DBPCFC1, but with additional doses of 1000 mg and 3000 mg for a cumulative dose of 4443 mg peanut protein. DBPCFC3 will follow a slightly different schedule of doses: 30 mg, 100 mg, 300 mg, 1000 mg, and 3000 mg for a cumulative dose of 4430 mg peanut protein.

If the participant has a subjective reaction to one of the doses, the study nurse may repeat that dose or consult with the supervising physician. If symptoms do not recur, the study nurse will continue the DBPCFC protocol after confirming with the supervising physician. If the study nurse is unsure about how to proceed, the supervising physician will be consulted to determine the appropriate action. Food challenges will be immediately stopped and the participant promptly treated for objective signs and symptoms as indicated in Figure 15.4, consistent with the 2010 NIAID-sponsored expert guidelines for the diagnosis and management of food allergies [?].

After the final dose of each challenge or the resolution of any suspected reaction symptoms, the participant will be observed for a minimum of 2 additional hours.

All food challenges will be performed under direct physician supervision. The supervising physician may stop a challenge if he/she feels it is in the best interest of the participant. Incomplete or indeterminate challenges will be rescheduled.

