9 SAMPLE SIZE CALCULATIONS AND STATISTICAL PLAN

9.1 Sample Size and Power Calculations

As the hypothesis regarding Treg induction and clonal tolerance can only be defined among those individuals who achieve desensitization and go on to DBPCFC3, the analysis will be per protocol for those participants who complete both post treatment challenges. The difference in the proportion of Treg will be compared between the groups using Students t test for comparison of means. Because we are expecting the primary outcome variable (difference in the proportion of Treg) to be log-normally distributed, we plan to carry out the t test on the log transformed variable. We will be powered at the expected effect on Treg if as few as six individuals (20% clinical effect and 10% dropout) who complete the protocol achieve our defined measure of at least partial clinical tolerance. Table 15.6 shows power calculations around these assumptions using a two sided t test at an alpha level of 0.05.

The sample size selected is 30 active treatment and 10 placebo treatment. We are applying the following assumptions for our power analysis (see Figure 15.5 for schema of assumptions).

- Approximately 27% of the Active Treatment group (8/30) will achieve Partial Tolerance (ED at DBPCFC3 <4430 mg but ≥430 mg AND >10-fold more than at DBPCFC1) or Full Tolerance (no reaction at DBPCFC3).
- The comparison of interest is between the combined Tolerance/Partial Tolerance and Active Treatment Failure groups who complete DBPCFC3.
- Those who fail to become desensitized after active treatment and those who receive placebo treatment are not fully informative for the primary endpoint and are therefore excluded for the per protocol analysis.
- The difference from baseline to the end of maintenance therapy in the mean proportion of induced Treg (CD45RA- CD25++ FoxP3++ of CD4+ T cells) between the Tolerance/Partial Tolerance and Treatment Failure groups will be 1.5 times the standard deviation.

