9.2.4 Study Endpoints

9.2.4.1 Primary Endpoint The difference in the proportion of induced Treg cells (CD45RA- CD25++ FoxP3++ of CD4+ T cells) from baseline to the end of maintenance therapy.

9.2.4.1.1 Clinical outcomes will be defined as follows:

- Treatment Failure: Failure to achieve the minimum maintenance dose (600 mg) of peanut protein by 12 months, or an ED <1443 mg at DBPCFC2, or ED at DBPCFC3 <430 mg OR <10-fold more than at DBPCFC1.
- Partial Tolerance: ED at DBPCFC3 <4430 mg but ≥430 mg AND >10-fold more than at DBPCFC1.
- Tolerance: Ingestion of 4430 mg of peanut protein at DBPCFC3 without symptoms.

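### Eliciting dose is undefined when a challenge dose is repeated, so entry rules can conflict, one repeat can change the outcome group, and some DBPCFC3 results fit no group

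*Combined protocol and SAP*

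**What the plan says.** **Challenge conduct (Section 7.7.1).** At DBPCFC1, "the first ingested dose will be 3 mg, then increasing to 10 mg, 30 mg, 100 mg, and 300 mg of peanut protein". DBPCFC2 adds 1000 and 3000 mg. DBPCFC3 uses 30, 100, 300, 1000 and 3000 mg. After a subjective reaction, "the study nurse may repeat that dose or consult with the supervising physician". Then: "If symptoms do not recur, the study nurse will continue the DBPCFC protocol after confirming with the supervising physician". The stopping rule is: "Food challenges will be immediately stopped and the participant promptly treated for objective signs and symptoms". The supervising physician may also stop a challenge, and incomplete or indeterminate challenges are rescheduled; indeterminate is not defined.

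**Entry.** Section 4.1 requires: "React to ≤443 mg of peanut protein during DBPCFC1". Section 7.4.1 randomises by dose step: "If the participant reacts at the 300 mg dose of peanut protein or less (443 mg cumulative", with the milligram figure in brackets. Section 3 gives the cut as a cumulative amount.

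**Outcome groups.** Sections 3.1.1 and 9.2.4.1.1 define Partial Tolerance as a DBPCFC3 ED of at least 430 mg and below 4430 mg that is more than 10-fold the DBPCFC1 value. Treatment Failure includes a DBPCFC3 ED less than 10-fold the DBPCFC1 value or below a floor. The floor is 443 mg in Section 3.1.1 and 430 mg in Section 9.2.4.1.1. Tolerance is "Ingestion of 4430 mg of peanut protein at DBPCFC3 without symptoms" in both. Section 9.1 words it as "Full Tolerance (no reaction at DBPCFC3".

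The glossary expands ED as eliciting dose and goes no further. Nothing says whether ED is cumulative or single-step, whether subjective symptoms set it, or how a repeated dose is scored.

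**The concern.** ED decides who is randomised, the fold change, and which side of the primary comparison a participant falls on. The primary test compares Treg change between the combined Tolerance/Partial Tolerance group and active Treatment Failures, with 8 and 14 expected. If repeated doses are added, ED rises although the participant reacts at the same step, so a discretionary repeat can settle eligibility or group membership with no change in sensitivity. Separately, if the groups do not cover every possible DBPCFC3 result, some participants in the per-protocol sample have no defined place in the primary test.

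**Working it through.** **1. The cut-offs are no-repeat sums** (doses from Section 7.7.1).

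- DBPCFC1: 3, 13, 43, 143, 443 mg cumulative.
- DBPCFC2: the same, then 443 + 1000 = 1443 and 1443 + 3000 = 4443 mg.
- DBPCFC3: 30, 130, 430, 1430, 4430 mg cumulative.

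**2. Entry.** For a DBPCFC1 reaction at the 300 mg step after one repeat, the total is 443 plus the repeated dose:

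| Repeated dose (mg) | 3 | 10 | 30 | 100 | 300 |
|---|---|---|---|---|---|
| Total (mg) | 446 | 453 | 473 | 543 | 743 |

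All five totals exceed the Section 4.1 limit and all five meet the step wording of Section 7.4.1. A reaction at the 100 mg step reaches at most 143 + 100 = 243 mg, so the conflict is confined to the 300 mg step.

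**3. Fold change without repeats.** Each DBPCFC3 cumulative value is exactly 10 times the DBPCFC1 value at the same position, so the 10-fold rule falls on ties. The ties 3/30 and 13/130 are Failures anyway, being below 430 mg. The ties 43/430, 143/1430 and 443/4430 are neither below nor above 10-fold.

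Classifying all 5 × 5 = 25 combinations of reacting step with no repeats gives:

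- Section 9.2.4.1.1: 7 have no group. These are the five with a reaction at the last DBPCFC3 step (4430 mg is not below 4430 mg and is not Tolerance), plus 43/430 and 143/1430.
- Section 3.1.1: 6 have no group (the same five, plus 143/1430). Two more, 3/430 and 13/430, meet both Failure (below 443) and Partial Tolerance (at least 430).

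**4. Effect of one repeat, if added.**

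- Section 9.2.4.1.1: the group changes in 3 of 25, all exact ties.
  - For 43/430 and 143/1430, a DBPCFC3 repeat gives Partial Tolerance: from 1460/143 = 10.2 to 730/43 = 17.0-fold.
  - For the same two, a DBPCFC1 repeat gives Failure: from 1430/146 = 9.8 down to 430/73 = 5.9-fold.
  - For 443/4430, a DBPCFC1 repeat gives Failure (4430/446 = 9.9 down to 4430/743 = 6.0). A DBPCFC3 repeat leaves it without a group.
- Section 3.1.1: 5 of 25. These are the same three combinations, plus 3/430 and 13/430, where a DBPCFC3 repeat (430 + 30 = 460 or more) clears the 443 mg floor. Here 43/430 starts as Failure and only a DBPCFC3 repeat moves it.
- No single repeat carries a lower step across the other cuts: at most 743 against 1443 mg (DBPCFC2, 300 mg step), 230 against 430 mg (DBPCFC3, 100 mg step), and 2430 against 4430 mg (DBPCFC3, 1000 mg step).

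**5. Finishing DBPCFC3 with subjective symptoms only.** With symptoms at the last step, Sections 3.1.1 and 9.2.4.1.1 give no group: the participant is not symptom-free, and an ED of 4430 is not below 4430. With symptoms at an earlier step only, there is no group if ED requires objective signs. If subjective symptoms set ED, that step assigns Failure or Partial Tolerance, ties apart. The no-reaction wording of Section 9.1 could make either participant Tolerant.

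**6. Power, for scale only.** For 8 v 14 at 1.5 SD, two-sided 0.05, the noncentrality is 1.5 × √(8 × 14/22) = 3.38 on 20 df. Power is 0.896, matching the 0.90 in Section 15.6. Assuming 1, 2 or 3 of the 8 cannot be placed, power is 0.867, 0.828 or 0.774. Assuming one participant is misplaced, the effect falls to 1.5 × 8/9 = 1.33 SD (9 v 13) or 1.5 × 14/15 = 1.40 SD (7 v 15), and power is about 0.83 either way.

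**The case against.** Section 7.7.1 is tighter than a free hand for the nurse. After a repeat the challenge goes on only if symptoms do not recur and the physician confirms, and indeterminate challenges are rescheduled. Section 7.4.1 can be read as treating 443 mg as the label of the 300 mg step, in which case a repeat alters nothing. Most of the trouble in the outcome groups comes from the ties and the 430/443 mismatch, not from repeats. All of this stands, and it limits the point. It does not remove it: the step reading of Section 7.4.1 is one half of the conflict with Section 4.1, and no text says which governs.

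Three stronger readings are tempting and are not supported:

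- *Repeats routinely move participants between groups.* They can do so in 3 or 5 of 25 combinations. Under Section 9.2.4.1.1 those three have no group to begin with.
- *Staff could steer the result.* Section 7.4.1 blinds nurse and physician to the challenge material at DBPCFC1, and Sections 7.4.5 and 7.4.7 describe the later challenges as the same kind of double-blind procedure. Haphazard misclassification is the more natural concern.
- *The best responders drop out and the trial loses power.* Section 9.2.2 keeps every active participant who completes DBPCFC3; what happens to one without a group is simply unstated. The number affected is unknown, and 0.83 lies within what the plan accepts (0.82 at 6 v 13 in Section 15.6).

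**Conclusion.** The point holds as a defect of definition. If repeats are added to ED, the entry rules contradict each other for any DBPCFC1 reaction at the 300 mg step after a repeat, and one repeat can change the group in 3 of 25 step combinations (Section 9.2.4.1.1) or 5 of 25 (Section 3.1.1). Whether or not repeats are added, the groups are not exhaustive: a last-step DBPCFC3 reaction, last-step subjective symptoms, and exact 10-fold ties at or above 430 mg have no place in Section 9.2.4.1.1. Section 3.1.1 has the same gaps, except that its 443 mg floor makes 43/430 a Failure, and it puts two combinations in two groups at once. For finishers whose subjective symptoms came earlier, the absence of a group depends on how ED is read.

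The combinations are counted, not weighted by how likely they are. The documents give no ED distribution for these challenges and no frequency of repeats or subjective symptoms, so the power figures are illustrative. The definitions should be settled before any participant is classified.

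**What to change.** - In Section 7.7.1, define ED as the scheduled cumulative dose at the reacting step, with repeats recorded but not added. Use it for entry and for every fold change. A repeat then changes entry or group in 0 of 25 combinations, and planned power stays at 0.896.
- Reconcile Sections 3, 4.1 and 7.4.1 on entry.
- Reconcile Sections 3.1.1, 9.1 and 9.2.4.1.1 on the 430/443 mg floor and on the two wordings of Tolerance.
- Make the groups exhaustive and exclusive, assigning an exactly 10-fold change and an ED of 4430 mg. Step scoring alone leaves both open.
- The sponsor decides which symptoms count toward ED and Tolerance, including in a challenge stopped for recurrent subjective symptoms, and states it once. This choice belongs to the sponsor because Section 5.6.1 ties later options to the DBPCFC3 result.
- Report completers with subjective symptoms only in a sensitivity analysis.

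The cost is a protocol amendment to wording, with no extra visits or samples and no change to when a dose is repeated or a challenge stopped. The scored ED will be somewhat below the amount swallowed when a dose was repeated; the recorded repeats show by how much.

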7.7.2 Immunotherapy Administration

Drug product will be prepared in the MGH CRC as described in Section 5.3. Participants will ingest daily dose of immunotherapy mixed with one of a few vehicle foods they may choose and which they will provide. The oral immunotherapy procedure consists of three phases: Modified Rush, Build Up, and Maintenance.

7.7.2.1 Modified Rush The modified rush procedure begins with 0.1 mg peanut protein-containing peanut powder or equivalent placebo, stirred in a vehicle food, approximately doubling the dose every 30 minutes until a maximum of 6 mg is tolerated (cumulative dose of 12 mg; Figure 15.2). Available vehicle foods will include rice milk, soymilk, mint chocolate mousse, or applesauce, depending on the participant's other allergies and p s. The MGH CRC will prepare all doses. This visit will occur within 2 weeks after the completion of DCPCFC1.

Participants will not have active wheezing or a current flare in atopic dermatitis. If symptoms occur preventing escalation to 6 mg, the highest tolerated dose (at least 1.5 mg) will be accepted as the dose for further escalation. Participants must tolerate at least 1.5 mg as a final dose to remain in the study.

Participants may develop symptoms during the initial escalation. For isolated oral or pharyngeal pruritus, the action should be to continue the normal dosing in 30 minutes. If symptoms are not limited to isolated oral or pharyngeal pruritus, the investigator's judgment will be required to determine the best course of action with possible actions being the following:

- 1. Extend time interval between dosing (up to an additional 30 minutes) and advance forward
- 2. Return to previously tolerated dose (i.e., repeat of last tolerated dose) then advance forward
- 3. Discontinue protocol and define the starting Build Up dose as the previously given dose

The Modified Rush procedure will be immediately stopped and the participant promptly treated for objective signs and symptoms as indicated in Figure 15.4, consistent with the 2010 NIAID-sponsored expert guidelines for the diagnosis and management of food allergies [?].

For a completed initial escalation protocol with no symptoms or only mild symptoms, subjects should have a 2-hour post-protocol observation period. For moderate to severe symptoms, the observation period will be extended based on the participants symptoms and the treatment regimen required to stabilize the participant.

7.7.2.2 Build Up Participants will then begin the starting dose for the Build Up phase of peanut flour or oat flour in an acceptable and tolerated food into which the powder can be stirred. The initial daily dose will be the highest dose tolerated during the modified rush phase on Day 1 (maximum 6 mg). To ensure there are no ill effects of the once daily dosing, the first daily dose of peanut or placebo will be given in the MGH CRC on Day 43 (one day after completion of the Modified Rush). Thereafter, the daily dose will be given at home from pre-aliquoted single dose portion cups, prepared by the MGH CRC dietitian. The participants will then be seen in the MGH CRC every two weeks (± 4 days) to follow the dosage escalation schedule according to Figure 15.3 to a target daily dose of 4000 mg of peanut protein.

Participants will be free from active wheezing or a flare of atopic dermatitis prior to any Build Up dose. Participants will be maintained on their current dose of study product until their flare of asthma or atopic dermatitis resolve. Participants may develop symptoms during the first administration of the new Build Up dose. The investigator's judgment will be required to determine the best course of action with possible actions being the following:

1. Continue with daily home dosing at the new Build Up dose

- 2. Continue with daily home dosing at the previously tolerated daily dose for the next (additional) 2-week interval
- 3. Return the following day for repeat trial at the new Build Up dose in the MGH CRC
- 4. Return the following day for dosing of previously tolerated dose (without escalation) in the MGH CRC
- 5. Discontinue dosing

If a participant has a Build Up dose in the MGH CRC without symptoms, the action should be to continue with daily home dosing of the new dose until the next Build Up visit at the MGH CRC two weeks later.

If the participant has a Build Up dose in the MGH CRC and experiences isolated oral/pharyngeal pruritus or very mild and self-limited symptoms, defined as:

- Skin: limited or localized hives/swelling, skin flushing or pruritus
- Respiratory: rhinorrhea/ sneezing, nasal congestion, occasional cough, throat discomfort
- GI: mild abdominal discomfort/ minor episode of vomiting

then the same dose can be repeated the next day at home and continued for the next two week interval unless other symptoms begin to develop at home (see below).

If the participant has a Build Up dose in the MGH CRC and experiences symptoms that require treatment in accordance with Figure 15.4, the patient will continue on the previously tolerated dose for the next two week interval.

Participants may also develop symptoms during the subsequent at home administrations of the Build Up doses. The participants will be instructed to contact study staff for any symptoms. The study physician's judgment will be required to determine the best course of action with possible actions being the following:

- 1. Continue with daily home dosing at the current Build Up dose
- 2. Continue with daily home dosing at the previously tolerated daily dose for the next (additional) 2-week interval
- 3. Return the following day to the MGH CRC for repeat trial at the current Build Up dose
- 4. Return the following day to the MGH CRC for dosing at a previously tolerated dose
- 5. Discontinue dosing

For reactions for which epinephrine was given (1-2 doses) or was indicated (as outlined in Figure 15.4), treatment will be withheld until it can be resumed (as below) in the MGH CRC. As per individual stopping rules (see section 8.1.2) participants who receive more than two doses of epinephrine for a single reaction will be withdrawn. For minor reactions (appropriately treated without epinephrine as outlined in Figure 15.4), treatment will be resumed at home unless the study physician determines that resumption should take place in the CRC.

Resumption of treatment will proceed as follows: 50% of the previously tolerated amount for 4-5 days, 75% for 4-5 days and then 100%. The previously scheduled Build Up visit will be postponed to take place 2 weeks (12 days minimum) after resumption of the 100% dose.

If a participant fails to tolerate 3 consecutive Build Up attempts prior to reaching 600 mg or if the participant fails to reach 600 mg by week 50, then the participant will be considered a treatment failure.

If the participant misses one or two days of the daily dose for any reason then he or she will continue on the same dose. If the participant misses the dose for three days, the participant will be asked to return to the MGH CRC for the next daily dose to ensure that there are no adverse effects from resuming dosing. If the participant misses their dose for four or more days, he/she will have to return to the MGH CRC for a modified rush protocol to escalate back to the highest previously tolerated dose beginning at 50%. For the duration of the study, the participant will be asked to continue to follow a peanut elimination diet.

7.7.2.3 Maintenance At the end of the Build Up phase, the participants will continue on the achieved daily dose for 12 weeks in the maintenance phase. Participants in a reported study have tolerated a very similar dosing schedule with minimal symptoms [?]. Participants will enter the Maintenance phase at the highest dose tolerated by week 50 (at least 600 mg).

Participants may develop symptoms during the at home administrations of the Maintenance doses. The participants will be instructed to contact study staff for any symptoms. The study physician's judgment will be required to determine the best course of action with possible actions being the following:

- 1. Continue with daily home dosing at the current Maintenance dose
- 2. Continue with daily home dosing at 50% of the Maintenance dose
- 3. Return the following day to the MGH CRC for observed trial at the current Maintenance dose
- 4. Return the following day to the MGH CRC for observed trial of a reduced dose (e.g. 50%, 75%)
- 5. Discontinue dosing

For reactions for which epinephrine was given (1-2 doses) or was indicated (as outlined in Figure 15.4), treatment will be withheld until it can be resumed (as below) in the MGH CRC. As per individual stopping rules (see section 8.1.2) participants who receive more than two doses of epinephrine for a single reaction will be withdrawn. For minor reactions (appropriately treated without epinephrine as outlined in Figure 15.4), treatment will be resumed at home unless the study physician determines that resumption should take place in the CRC.

Resumption of treatment will proceed as follows: 50% of the previously tolerated amount for 4-5 days, 75% for 4-5 days and then 100%. The previously scheduled Build Up visit will be postponed to take place 2 weeks (12 days minimum) after resumption of the 100% dose.

If the participant misses one or two days of the daily dose for any reason then he or she will continue on the same dose. If the participant misses the dose for three days, the participant will be asked to return to the MGH CRC for the next daily dose to ensure that there are no adverse effects from resuming dosing. If the participant misses their dose for four or more days, he/she will have to return to the MGH CRC for a modified rush protocol to escalate back to the highest previously tolerated dose beginning at 50%. For the duration of the study, the participant will be asked to continue to follow a peanut elimination diet.

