7.7.6 Phlebotomy

At visits 0, 27 and 30, 3ml/kg (for participants <18 years and/or participants weighing <50 kg) or 1 unit (550 ml) of blood will be obtained by standard venipuncture at the MGH blood bank. One (1) ml of blood will be used to measure peanut specific IgE, IgG, and IgG4. Five (5) ml of blood will be used to measure basophil activation. The remaining blood will be used for mechanistic T cell and B cell studies. Prior to each scheduled large blood draw, a rapid test of hemoglobin level will be performed.

The following criteria will be used to determine for adult participants whether the proposed 550 ml can be drawn:

- AGE must be at least 18 years old
- WEIGHT must be greater than 110 lbs (50 kg);
- PULSE must be between 50 and 100 beats/minute with no cardiac irregularity;
- TEMPERATURE must not exceed 37.55°C or 99.5°F;
- Hematocrit < 0.36 for adult females or < 0.38 for adult males;

An additional blood collection of \leq 200 ml (adults) and 3ml/kg (children) will occur after 12 weeks of treatment to be used for mechanistic B cell studies. For B cell studies, 100-200 million PBMCs will be used for affinity single-cell sorting of Arah2-specific B cells by flowcytometry (see Patil et al. 2015 JACI) as well as bulk sorting of CD19+ CD27+ IgM- cells. These will be used for cloning of functional mAbs and next generation sequencing of BCR, respectively.

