8.1.5 Participant Replacement

Participants who are permanently discontinued from the study during or after the Modified Rush will not be replaced.

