15.1 Study Schematic

15.2 Modified Rush Dosing Schedule

Dose no.	Peanut Dose (mg protein)	Cumulative Peanut Dose (mg protein)
1	0.1	0.1
2	0.2	0.3
3	0.4	0.7
4	0.8	1.5
5	1.5	3.0
6	*3.0	6.0
7	6.0	12
	* Minimum dose ne	cessary to continue

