15.3 Build Up Dosing Schedule

[figure not shown]
Note: Build Up dosing may begin at dose 7 if maximum tolerated at Modified Rush was 3 mg							
Dose no.	Dose (mg protein)	Interval (weeks)	% Increase				
8	12	2	1.0				
9	25	2	1.08				
10	50	2	1.00				
11	75	2	0.50				
12	100	2	0.33				
13	125	2	0.25				
14	160	2	0.28				
15	200	2	0.25				
16	245	2	0.23				
17	300	2	0.22				
18	385	2	0.28				
19	480	2	0.25				
20	600	2	0.25				
21	750	2	0.25				
22	940	2	0.25				
23	1200	2	0.28				
24	1465	2	0.22				
25	1830	2	0.25				
26	2285	2	0.25				
27	2860	2	0.25				
28	3575	2	0.25				
29	4000	2	0.12				

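### The Modified Rush minimum is 1.5 mg in Section 7.7.2.1 but 3.0 mg in Table 15.2, and the haematocrit line for the 550 ml draw in Section 7.7.6 carries exclusion wording

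*Combined protocol and SAP*

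**What the plan says.** **Modified Rush minimum.** Section 7.7.2.1 gives the lower limit twice. If symptoms prevent escalation to 6 mg, "the highest tolerated dose (at least 1.5 mg) will be accepted as the dose for further escalation". The next sentence makes it a condition of staying in: "Participants must tolerate at least 1.5 mg as a final dose to remain in the study". Table 15.2, to which Sections 7.4.2 and 7.7.2.1 both send staff for the dosing steps, puts an asterisk on the 3.0 mg entry of dose 6 in the single-dose column. Its footnote marks that as the smallest dose needed to continue. The note to Section 15.3 adds that "Build Up dosing may begin at dose 7 if maximum tolerated at Modified Rush was 3 mg". Section 8.1.5 states: "Participants who are permanently discontinued from the study during or after the Modified Rush will not be replaced".

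**Haematocrit for the large draw.** Section 7.7.6 introduces a list with the words "The following criteria will be used to determine for adult participants whether the proposed 550 ml can be drawn". The age, weight, pulse and temperature lines each state, with an explicit verb, what has to be true. The haematocrit line has no verb and gives below 0.36 for adult women and below 0.38 for adult men. Those are the limits that Section 4.2 and the synopsis use to exclude. Section 7.7.6 also requires a rapid haemoglobin test before each large draw, but no limit for it is readable.

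**The concern.** The first discrepancy concerns a withdrawal rule. Sections 7.1 and 7.4.1 place randomisation after the first food challenge, so a participant in the Modified Rush has already been allocated. Two members of staff could each follow the protocol and reach opposite decisions about the same person. A participant kept in goes on to daily peanut or placebo dosing; one removed is lost to the trial. Section 9.2.5 describes a primary-outcome analysis of those who complete the Modified Rush visit, so the rule that is applied may also change who is counted.

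The second concerns a safety limit. Section 1.6.2.4 names aggravation of existing anaemia as a risk of the blood draws, though it calls that risk negligible because of the volumes taken. The haematocrit exclusion in Section 4.2 applies at entry. For each later large draw, the readable safeguards are the haematocrit line in 7.7.6 and a haemoglobin test without a stated limit.

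**Working it through.** **1. Could 1.5 mg and 3.0 mg be one threshold on two scales?** The inputs are the single doses in Table 15.2. The formula is cumulative dose = previous cumulative dose + current single dose.

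| Dose no. | Single dose (mg) | Running sum (mg) | At least 1.5 mg (7.7.2.1) | At least 3.0 mg (Table 15.2) |
|---|---|---|---|---|
| 1 | 0.1 | 0.1 | leaves | leaves |
| 2 | 0.2 | 0.1 + 0.2 = 0.3 | leaves | leaves |
| 3 | 0.4 | 0.3 + 0.4 = 0.7 | leaves | leaves |
| 4 | 0.8 | 0.7 + 0.8 = 1.5 | leaves | leaves |
| 5 | 1.5 | 1.5 + 1.5 = 3.0 | **stays** | **leaves** |
| 6 | 3.0* | 3.0 + 3.0 = 6.0 | stays | stays |
| 7 | 6.0 | 6.0 + 6.0 = 12.0 | stays | stays |

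The running sums reproduce the cumulative column of Table 15.2, and the last one agrees with the 12 mg given in 7.7.2.1. The rows as read are therefore not shifted.

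- If the starred 3.0 were a cumulative dose, it would correspond to dose 5 and match the text. But the asterisk is on the single dose of row 6, whose cumulative dose is 6.0 mg.
- If the 1.5 mg in the text were cumulative, it would correspond to dose 4 (0.8 mg single), which widens the gap. The text also speaks of a final dose, which is a single dose.

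Neither reading reconciles the two. The rules are one dose step apart (3.0 / 1.5 = 2-fold) and disagree at dose 5 only.

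**2. Can a participant end at dose 5?** Yes, by the protocol's own steps. If symptoms occur at 3.0 mg, the third action open to the investigator in 7.7.2.1 is: "Discontinue protocol and define the starting Build Up dose as the previously given dose". The previously given dose is then 1.5 mg. The text starts Build Up there, while the table ends participation.

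**3. Does the 15.3 note settle it?** No. It covers a participant whose maximum was 3 mg, and 3 mg passes both rules. The readable rows of 15.3 start at dose 8 and part of that section is a figure not shown, so the lack of a readable 1.5 mg entry is not evidence.

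**4. The haematocrit line beside its neighbours.** No arithmetic applies.

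| Line in 7.7.6 | Values listed | Draw intended at those values? |
|---|---|---|
| Age | at least 18 years | yes |
| Weight | above 50 kg | yes |
| Pulse | 50 to 100 per minute, regular | yes |
| Temperature | no higher than 37.55 °C | yes |
| Haematocrit | below 0.36 (women), below 0.38 (men) | no: the Section 4.2 exclusion range |

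Four lines describe who may be drawn, and the fifth describes who should not be.

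**The case against.** The strongest reply on the first item is that 7.7.2.1 already gives a usable rule, stated twice, and that only one of seven dose steps is affected, perhaps in no participant at all. The size of that objection stands. But Table 15.2 is the sheet from which the visit is run, and its footnote says something else.

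A reader might infer that 3.0 mg is the intended value because the 15.3 note also mentions 3 mg. The note is compatible with both rules, so the documents do not support that choice. A reader might also take a frequency from Section 1.6.1, where the oldest group in an earlier study had an eliciting-dose interquartile range of 4.5 to 200 mg. That makes symptoms at 3.0 mg (cumulative 6.0 mg) plausible, but the population and dosing differ and it gives no rate for this trial.

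On the second item, the reply is that the haematocrit line lacks the verb that the others carry, so it can be read as a reason to defer the draw. This has force. A reader might infer that the protocol requires a low haematocrit and bars the draw in every eligible adult. That follows only if the missing verb is supplied, and nobody would apply it so. What stands is that a list of criteria should not change direction on its last line without saying so.

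A reader might also take visit 0 in 7.7.6 to be screening and conclude that only some of the large draws come after the entry check. Section 7.2 takes 10 ml at screening, while Section 7.3 and the Schedule of Events put the first mechanistic draw at Day 0. On that schedule all three large draws follow screening.

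**Conclusion.** Both points hold as inconsistencies in the current text, of minor to moderate weight.

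- **Modified Rush minimum:** a real conflict between 7.7.2.1 and Table 15.2, confined to participants whose highest tolerated dose is 1.5 mg. This assumes that the asterisk is printed on the dose 6 single dose, as the text extraction shows and the running sums support.
- **Haematocrit line:** a wording error with clear intent. Its weight comes from being a safety limit and from the haemoglobin test having no readable cut-off. It concerns adults only.

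Neither threshold is an input to the power calculation in Table 15.6. A reader might infer from this that the analysis is untouched. The documents do not show that: with no replacement and an analysis set defined by completing the Modified Rush (9.2.5), the minimum chosen may change who is analysed, by an amount that cannot be estimated from them.

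**What to change.** 1. With clinical sign-off, use one Modified Rush minimum in both places. Either keep 1.5 mg and move the Table 15.2 asterisk to dose 5, or change both 1.5 mg statements in 7.7.2.1 to 3.0 mg. Then check that the Build Up entry rows and note in 15.3 provide for every starting dose the rule allows.
2. Replace the haematocrit line in 7.7.6 with: Hematocrit must be at least 0.36 (adult females) or at least 0.38 (adult males). Add a sentence saying how the rapid haemoglobin result is judged against this before each large draw.

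The cost is one protocol clarification, with no new procedures and no additional participants.
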